10.3 Exploratory Efficacy Endpoints

The exploratory efficacy endpoints are as follows:

1. Change from baseline in Fugl-Meyer Motor Scale (FMMS) score at Week 24 among patients with both upper and lower extremity deficits
2. Change from baseline in Fugl-Meyer Motor upper-extremity subscale (UE-FM) score at Week 24 among upper extremity deficit patients
3. Change from baseline in Fugl-Meyer Motor lower-extremity subscale (LE-FM) score at

- Week 24 among lower extremity deficit patients
4. Improvement by ≥ 6 points at Week 24 from Baseline in UE-FM score among upper extremity deficit patients
 5. Improvement by ≥ 3 points at Week 24 from Baseline in LE-FM score among lower extremity deficit patients
 6. Improvement from Baseline by ≥ 10 points at Week 24 in Fugl-Meyer Motor Scale (FMMS) score among all patients
 7. Improvement from Baseline by ≥ 6 points at Week 24 in Action Research Arm Test (ARAT) score among upper extremity deficit patients
 8. Improvement from Baseline of at least one functional level [e.g., from < 0.4 m/s to 0.4-0.8 m/s or from 0.4 - 0.8 m/s to > 0.8 m/s] at Week 24 in Gait Velocity on standard 10 m walk among lower extremity deficit patients
 9. Pre- and post-contrast standard T1 and T2 weighted, dual echo, and FLAIR-MRI among all patients
 10. Perfusion MRI among all patients
 11. Diffusion tensor imaging (DTI) with tractography among all patients
 12. Lower limb motion as measured by leg activity monitor among lower extremity deficit patients (applicable for US and Japan only)
 13. Outcome analysis among all patients based on genotyping of polymorphisms at 3 specific loci:
 - HLA – degree of donor/recipient mismatch
 - BDNF Val66Met mutation present (yes/no)
 - ApoE (i.e., homo and heterozygosity for ApoE2, ApoE3, ApoE4 alleles)

The first three exploratory efficacy endpoints will each be analyzed in a manner analogous to that for the primary efficacy endpoint. In addition, each of these exploratory efficacy endpoints will be analyzed to examine dose response. Analogous statistical methodologies to those used for evaluating dose response for the primary efficacy endpoint will be used for these endpoints.

The fourth, fifth, sixth, seventh, and eighth exploratory efficacy endpoints will be summarized using frequencies and percentages and will be analyzed using a logistic regression model with a term for treatment (SB623 or sham surgery) and the baseline value of the endpoint and the GOS-E score at screening as continuous covariates.

The analyses of the last five exploratory efficacy endpoints will be addressed in separate documents.

10.4 Other Efficacy Analyses

The Fugl-Meyer Motor Scale 33-item upper-extremity subscale (UE-FM) score, the 17-item lower-extremity subscale (LE-FM) score, and the FMMS total score will be summarized by visit using descriptive statistics.

The DRS total score and the eight areas of functioning (eye opening, communication ability, motor response, feeding, toileting, grooming, level of functioning, and employability) will be summarized by visit using descriptive statistics.

The ARAT total score, gait velocity (i.e., 10 meter walk time), the two NeuroQOL subdomain T scores (Upper Extremity Function and Lower Extremity Function), and the Global Rating of

Perceived Change (from Baseline) by both Subject and Clinician will each be summarized by visit using descriptive statistics.

Graphs will be presented summarizing the mean value over time by treatment group (pooled SB623 and control) for the following variables: change from baseline in FMMS total score, change from baseline in DRS total score, change from baseline in ARAT total score, changes from baseline in the two NeuroQOL subdomain T scores, change from baseline in gait velocity, change from baseline in the UE-FM score, change from baseline in the LE-FM score, and the Global Rating of Perceived Change (from Baseline) by both Subject and Clinician. The graphs will plot the mean changes (\pm standard error) over time. The graphs will also present the p-value at each post-baseline timepoint from a two-sample t-test testing the null hypothesis that the true mean change is equal for the two treatments. Similar graphs will be presented by SB623 dose group, but no p-values will be presented.

In order to investigate the magnitude of effect that might be indicative of clinical meaningfulness, Receiver Operating Characteristic (ROC) curves based on responder status will be plotted for the change from Baseline to Week 24 in the following endpoints: FMMS score among all patients, UE-FM score among upper extremity deficit patients, LE-FM score among lower extremity deficit patients (for both methods of imputing missing baseline values for the previous endpoints), ARAT total score among upper extremity deficit patients, gait velocity among lower extremity deficit patients, and the two NeuroQOL subdomain T scores (Upper Extremity Function and Lower Extremity Function) among upper extremity deficit and lower extremity deficit patients, respectively. These ROC curves will be based on the following definition of a responder. A subject will be considered a responder if the subject's Global Rating of Perceived Change from Baseline at Week 24 is ≥ 6 . Separate analyses will be done for GRPC-S and GRPC-C. For each of the GRPC versions (GRPC-S and GRPC-C), a table will be produced summarizing the area under the ROC curve (AUC) for each endpoint. The purpose of the ROC curve analyses is to see how predictive each of the endpoints are of the clinical benefit as perceived by the subject and the clinician.

To further investigate clinical meaningfulness, the primary and secondary efficacy endpoints, except the global ratings endpoints, will be summarized using descriptive statistics for the following groups:

- Global Rating of Perceived Change from Baseline at Week 24 - Subject ($\leq 5, \geq 6$)
- Global Rating of Perceived Change from Baseline at Week 24 - Clinician ($\leq 5, \geq 6$)

Graphs of the sample cumulative distribution functions (CDFs) will be produced by treatment (pooled SB623 and Control) for the change from baseline to Week 24 for each of the endpoints listed in the paragraph above discussing ROC curves. These graphs will show the probability of being x or better with 'better' values being to the right on the x-axis, so that for endpoints for which larger values are better (all of the endpoints except gait velocity), the graph will be of 1 - CDF, i.e., $P(X \geq x)$, rather than the CDF. These figures will allow one to compare response rates between treatments for all possible cut-off values for defining response. The Kolmogorov-Smirnov Test will be used to test the null hypothesis that the true CDFs are equal for the two treatments.

The change from baseline in Gait Velocity (10 meter walk time in seconds) to each post-baseline visit among lower extremity deficit patients will also be analyzed using the Wilcoxon rank sum

test to test the null hypothesis that the true mean changes are equal for the two treatments. In addition, for each treatment group, a shift table of frequencies and percentages will be presented summarizing changes in walk time status (< 300 seconds vs. ≥ 300 seconds) from Baseline to each post-baseline visit. McNemar's Test will be used to test the null hypothesis that the true probability of a walk time < 300 seconds is equal at Baseline and the post-baseline visit. For these analyses, for walk times recorded with a value of '999', a blinded review will be performed of the reason the test was not performed. If the subject could not take the test because they were not mobile, they will be assigned a walk time of 300 seconds. If the reason the test was not performed was not related to the subject's ambulatory status, the walk time will be considered missing and the subject will be excluded from the analysis.

12.0 SAFETY ANALYSES

12.1 Adverse Events

All safety analyses will be performed on the safety population.

The summary of AEs will be limited to treatment emergent AEs, which are defined as any adverse event with onset on or after the initiation of treatment or any adverse event already present that worsens in intensity following exposure to study treatment.

The number and percentage of subjects with at least one adverse event, at least one serious adverse event (SAE), and at least one adverse event that led to discontinuation from the study will be presented. The number and percentage of subjects having an adverse event in each System Organ Class (SOC) and having each individual type of adverse event (Preferred Term) will be presented. Fisher's Exact Test will be used to test for differences between treatments (pooled SB623 vs. sham surgery) in the proportion of subjects experiencing AEs in each SOC. This analysis will also be performed for SAEs, except that no statistical testing will be performed. Adverse events will also be summarized at the event level by SOC/Preferred Term and severity, by SOC/Preferred Term and relationship to study product, by SOC/Preferred Term and relationship to surgery, and by SOC/Preferred Term and action taken.

12.2 Laboratory Tests

Descriptive statistics will be presented by visit for the actual values and the changes from baseline for each quantitative laboratory test (hematology, serum chemistry, and INR) . The difference between treatment groups (pooled SB623 - sham surgery) in the mean change from baseline will also be presented. For each laboratory test, the one- sample t-test will be used to test whether the mean change from baseline equals 0 for each post-baseline time point. The two-sample t-test will be used to test whether the mean changes from baseline are equal for the two treatments (pooled SB623 vs. sham surgery). Shift tables will summarize changes in status (normal, abnormal) from baseline to each post-baseline time point for each laboratory test. Abnormal lab values will be flagged in the data listings.

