7.2 Exclusion Criteria

- 1. History or presence of any other major neurological disease
- 2. Any seizures in the prior 3 months
- 3. The presence of contracture at any joints that would interfere with interpretation of any of the neurological assessments (*e.g.*, contracture preventing the detection of any increase in the range of motion or ability to perform a task)
- 4. Other neurologic, neuromuscular or orthopedic disease that limits motor function
- 5. Clinically significant finding on MRI of brain not related to TBI
- 6. Known presence of any malignancy except squamous or basal cell carcinoma of the skin
- 7. History of CNS malignancy
- 8. Positive findings on tests for occult malignancy, unless a non-malignant etiology is confirmed

- 9. Uncontrolled systemic illness, including, but not limited to: hypertension (systolic >150 mm Hg or diastolic >95 mm Hg); diabetes; renal, hepatic, or cardiac failure
- 10. Uncontrolled major psychiatric illness, including depression symptoms (CESD-R Scale of ≥16)
- 11. Total bilirubin >1.9 mg/dL
- 12. Serum creatinine >1.5 mg/dL
- 13. Hemoglobin <10.0 g/dL
- 14. Absolute neutrophil count <2000/mm³
- 15. Absolute lymphocytes <800/mm³
- 16. Platelet count $<100,000/\text{mm}^3$
- 17. Liver disease documented by AST (SGOT) or ALT (SGPT) ≥2.5 x institutional upper limit of normal
- 18. Serum calcium >11.5 mg/dl
- 19. Unexplained abnormal preoperative test values (blood tests, electrocardiogram [ECG], chest X-ray); x-ray evidence of infection; uncontrolled atrial fibrillation or uncontrolled congestive heart failure
- 20. Presence of craniectomy (without bone flap replacement) or other contraindication to stereotactic surgery
- 21. Participation in any other investigational trial within 4 weeks of initial screening or within 7 weeks of study entry
- 22. Botulinum toxin injection, phenol injection, intrathecal baclofen, or any other interventional treatments for spasticity (except bracing and splinting) within 16 weeks of the Baseline visit. (interventional treatment refers to treatment done with special equipment which is typically performed in a surgical or procedural type facility this does not apply to oral medications such as oral baclofen).
- 23. Ongoing use of herbal or other non-traditional drugs
- 24. Substance use disorder (per DSM-V criteria, including drug or alcohol)
- 25. Contraindications to head CT or MRI
- 26. Pregnant or lactating

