18.3 Analysis of Safety

All safety analyses will be performed on the safety population.

Adverse events (AEs) will be summarized by presenting, for each treatment group, the number and percentage of patients having any adverse events, having an adverse event that led to

Confidential and Proprietary

discontinuation from the study, having an adverse event in each System Organ Class (SOC) and having each individual type of adverse event (Preferred Term). These analyses will also be performed for serious adverse events (SAEs). Adverse events will also be summarized at the event level by severity, by relationship to study product or surgery, and by action taken. Other information collected will be listed. The summary of AEs will be limited to treatment emergent AEs (TEAEs), which are defined as any adverse event with onset on or after the initiation of treatment or any adverse event already present that worsens in intensity following exposure to study treatment.

For each treatment group, descriptive statistics will be presented by visit for the actual values and the changes from baseline for each quantitative laboratory test. The difference between treatment groups in the mean change from baseline will also be presented. For each laboratory test and each treatment group, the one- sample t-test will be used to test whether the mean change from baseline equals 0 for each post-baseline time point. The two-sample t-test will be used to test whether the mean changes from baseline are equal for the two treatments. A shift table will summarize changes in status (normal, abnormal) from baseline to each post-baseline time point for each laboratory test, and abnormal lab values will be flagged in the data listings.

For each treatment group, descriptive statistics will be presented by visit for the actual values and the changes from baseline for each vital sign. The difference between treatment groups in the mean change from baseline will also be presented. For each vital sign and each treatment group, the one-sample t-test will be used to test whether the mean change from baseline equals 0 for each post-baseline time point. The two-sample t-test will be used to test whether the mean changes from baseline are equal for the two treatments. A shift table will summarize changes in status (normal, abnormal) from baseline to each post-baseline time point for each vital sign, and abnormal values will be flagged in the data listings.

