21.0 APPENDIX B: WHO STANDARD TOXICITY CRITERIA

The WHO Standard Toxicity Criteria is tabulated below in Table 5.

Copies of this document will also be provided to each site as part of the study documents.

For abnormalities not found elsewhere in the WHO table, use the following scale to assign grade or severity:

Grade 1	Mild	Transient of mild discomfort; no limitation in activity; no medical intervention/therapy required.
Grade 2	Moderate	Mild-to-moderate limitation in activity; some assistance may be need. No or minimal medial intervention/therapy required.
Grade 3	Severe	Marked limitation in activity, some assistance usually required; medical intervention/therapy required; hospitalization or prolongation of current hospitalization possible.
Grade 4	Life-threatening	Extreme limitation in activity, significant assistance required; significant medial intervention/therapy required; hospitalization or prolongation of current hospitalization or hospice care probable.

Confidential and Proprietary

Catagomy	Torioity	Grade 0	Grade 1	Grade 2	Grade 3	Grade 4
Category	Toxicity					
Haematology	WBC $(x10^{3}/l)$	4	3.0 - 3.9	2.0 - 2.9	1.0 - 1.9	< 1.0
Haematology	Platelets $(x10^3/l)$	WNL	75.0 - normal	50.0 - 74.9	25.0 - 49.9	< 25.0
Haematology	Haemoglobin (g/dl)	WNL	10.0 - normal	8.0 - 9.9	6.5 - 7.9	< 6.5
Haematology	Granulocytes/ Bands (x10 ³ /l)	2	1.5 - 1.9	1.0 - 1.4	0.5 - 0.9	< 0.5
Haematology	Lymphocytes $(x10^{3}/l)$	2	1.5 - 1.9	1.0 - 1.4	0.5 - 0.9	< 0.5
Haematology	Haemorrhage	none	mild, no	gross, 1 - 2 units transfusion per episode	gross, 3 - 4 units transfusion per episode	massive, > 4 units transfusion per episode
Coagulation	Fibrinogen	WNL	0.99 - 0.75 x N	0.74 - 0.50 x N	0.49 - 0.25 x N	< 0.25 x N
Coagulation	Prothrombin time(Quick)	WNL	1.01 - 1.25 x N	1.26 - 1.50 x N	1.51 - 2.00 x N	> 2.00 x N
Coagulation	Partial thromboplastin time	WNL	1.01 - 1.66 x N	1.67 - 2.33 x N	2.34 - 3.00 x N	> 3.00 x N
Metabolic	Hyperglycaemia (mg/dl)	< 116	116 - 160	161 - 250	251 - 500	> 500 or ketoacidosis
Metabolic	Hypoglycaemia (mg/dl)	> 64	55 - 64	40 - 54	30 - 39	< 30
Metabolic	Amylase	WNL	< 1.5 x N	1.5 - 2.0 x N	2.1 - 5.0 N	> 5.0 x N
Metabolic	Hypercalcaemia (mg/dl)	< 10.6	10.6 - 11.5	11.6 - 12.5	12.6 - 13.4	13.5
Metabolic	Hypocalcaemia (mg/dl)	> 8.4	8.4 - 7.8	7.7 - 7.0	6.9 - 6.1	6

 Table 5
 WHO (World Health Organization) Toxicity Criteria by Grade

Category	Toxicity	Grade 0	Grade 1	Grade 2	Grade 3	Grade 4

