5.0 STATISTICAL CONSIDERATIONS

5.1 General Methodology

The statistical analysis of the data obtained from this study will be performed using SAS[®] version 9.4 or higher. All statistical tests will be performed at the 0.05 significance level.

The data collected in this study will be documented using summary tables and subject data listings. Continuous variables will be summarized using descriptive statistics, specifically the number of observations, mean, median, standard deviation, minimum and maximum. Categorical variables will be summarized by frequencies and percentages. For the most part results will be presented for the four treatment groups separately and the three SB623 dose groups pooled. The three SB623 dose groups will be pooled for all statistical tests comparing SB623 to sham surgery, except where noted otherwise (i.e., dose response analyses).

Data listings will be sorted by center and subject ID. All date fields will be presented in a format of ddmmmyyyy (i.e., 01Jan2018) in the listings.

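### The laboratory shift tables merge low and high values into one abnormal class, so no listed output counts by arm the patients who become newly low or newly high

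*SAP*

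**What the plan says.** SAP 12.2 sets the rule: "Shift tables will summarize changes in status (normal, abnormal) from baseline to each post-baseline time point for each laboratory test". It takes this over from Protocol 18.3: "A shift table will summarize changes in status (normal, abnormal) from baseline to each post-baseline time point for each laboratory test". Neither section divides the abnormal class by direction.

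The same SAP section plans other laboratory output:

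- "Descriptive statistics will be presented by visit for the actual values and the changes from baseline for each quantitative laboratory test". SAP 5.1 defines descriptive statistics as "specifically the number of observations, mean, median, standard deviation, minimum and maximum".
- "The difference between treatment groups (pooled SB623 - sham surgery) in the mean change from baseline will also be presented", with one-sample and two-sample t-tests.
- "Abnormal lab values will be flagged in the data listings". The text does not say whether the flag shows low or high.

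The combined SAP's list of tables gives five laboratory outputs, 14.3.4.1 to 14.3.4.5: values and changes for hematology, serum chemistry and INR, and shift tables for hematology (14.3.4.2) and serum chemistry (14.3.4.4). The table shells are not in the supplied text.

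Under Protocol 16.1, a laboratory abnormality that the investigator judges clinically significant and that is worse than at baseline counts as an adverse event. SAP 12.1 tabulates adverse events by patient and Preferred Term.

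**The concern.** For many of these tests, low and high point to different problems, and the documents respect that elsewhere. Protocol 7.2 excludes on low counts, for example "Absolute lymphocytes <800/mm³", but on high calcium, creatinine and bilirubin. Protocol Appendix B grades high and low calcium on separate rows. SAP 12.3, Table 4, separates fast from slow heart rate and high from low systolic pressure. The laboratory shift table makes no such split.

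At stake is whether a reader of the safety tables can see how many patients in each arm developed, say, a high rather than a low white cell count after an intracranial implant of allogeneic cells. Hematology and serum chemistry are named safety endpoints in Protocol 5.2.2 and SAP 4.4, so this is a question the report should be able to answer with a count.

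**Working it through.** The plan gives no figure on this point, so there is none to reproduce. The check has three steps. It assumes that abnormal means outside the laboratory's reference range.

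**1. What the two-state rule merges.** A low/normal/high scale has 3 × 3 = 9 transitions from baseline to a later visit. Collapsed to normal/abnormal they become 4 cells:

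| Cell in the planned table | Transitions it contains |
|---|---|
| normal to normal | normal–normal |
| normal to abnormal | normal–low, normal–high |
| abnormal to normal | low–normal, high–normal |
| abnormal to abnormal | low–low, low–high, high–low, high–high |

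A new low and a new high therefore share a cell, and a complete reversal shares a cell with no change.

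**2. Which tests are affected.** Protocol 15.3 lists 6 hematology tests and 11 chemistry tests, 17 in all. On my reading, 11 have two directions of interest: the 6 hematology tests plus sodium, chloride, calcium, potassium and magnesium (6 + 5 = 11). For the other 6 (creatinine, BUN, AST, ALT, alkaline phosphatase, bilirubin) one direction dominates and the split adds little.

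**3. Whether the other outputs supply the missing count.** With 52 patients at 3:1, the arms hold about 52 × 3/4 = 39 and 52 × 1/4 = 13. The following numbers are assumed, for illustration only. In the SB623 arm, 4 patients go from normal to high by an amount d, 4 go from normal to low by the same amount, and the other 31 average no change.

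- Mean change = (4d − 4d + 31 × 0)/39 = 0.
- Shift table, normal to abnormal = (4 + 4)/39 = 8/39 = 20.5%.
- If all 8 had gone high, the shift table would again show 8/39, while the mean change would be 8d/39 = 0.21d.

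So when movement within an arm is mixed, the mean shows nothing and the shift table shows a number without direction. The minimum and maximum show one value at each end, not how many patients crossed a limit. They are also hard to compare between arms of unequal size: with no treatment effect and exchangeable values, the larger arm holds the overall extreme with probability 39/52 = 75%.

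**The case against.** The strongest reply is that direction remains visible. Changes from baseline are signed, the between-group difference is signed, extremes are reported for each test and visit, abnormal values are flagged by patient, and abnormalities judged clinically significant reach the adverse event tables. All of this stands. A reader might infer from the two-state rule that the plan hides the direction of laboratory harm, or that the shift table is the only patient-level laboratory summary. The documents support neither reading.

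Nor would opposite movement in the two arms necessarily be missed. If 20% of SB623 patients went high by d and 20% of sham patients went low by d, with the rest stable on average, the shift table would show 20% in each arm. The planned difference in mean change, however, would be 0.2d − (−0.2d) = 0.4d. The real gap is movement in both directions within an arm.

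Low-to-high swings may also be rare. Protocol 7.2 removes several out-of-range baselines and any unexplained abnormal preoperative results, and the documents give no frequency for those that remain. Sharing a cell between new lows and new highs is the more practical problem.

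The remaining arguments stand only in part. Adverse event reporting depends on investigator judgment, and Appendix B grades white cells, platelets, granulocytes and lymphocytes in the low direction only. A flagged listing is not a summary by arm. Finally, the shells for Tables 14.3.4.2 and 14.3.4.4 cannot be seen, so a split there can be neither confirmed nor excluded.

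**Conclusion.** The point holds, at low severity. As written in both documents, the laboratory shift tables cannot separate new lows from new highs, and they place reversals with unchanged abnormal results. None of the five listed laboratory tables is described as counting newly low or newly high patients by arm, and the means do not replace that count when patients within an arm move both ways.

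The size cannot be estimated from the documents, because they give no rate of out-of-range results; 8/39 is an illustration only. The conclusion rests on the wording of SAP 12.2 and Protocol 18.3 and on the table titles. It would reduce to a wording correction if the shells already split low from high. The SAP agrees with the protocol here, so there is no contradiction between them. No primary analysis, power, alpha or decision rule depends on these tables.

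**What to change.** In SAP 12.2, and in Tables 14.3.4.2 and 14.3.4.4, define each result as low, normal or high against the central laboratory's reference range, and present shifts from baseline to each visit by arm. Do this at least for the hematology panel, sodium, chloride, potassium, calcium and magnesium. If the two-state layout is kept, add separate rows for normal-to-low and normal-to-high. State in 12.2 that the listing flags show low or high. If the shells already make the split, bring the 12.2 wording into line with them.

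Because Protocol 18.3 names two states, record the change in SAP 3.5. The main SAP addendum shows that interim results have been unblinded, so label it as a later refinement of a descriptive display. The two-state table can still be recovered by adding cells.

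The cost is a few sentences and two table programs. No new data are needed, since calling a result abnormal already requires a reference range. The downside is larger tables (9 cells instead of 4) with many sparse cells, especially in a sham arm of about 13.
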